5. STUDY OBJECTIVES AND ENDPOINTS

5.1 Study Objectives

The objectives of the study are to assess safety, tolerability, preliminary efficacy and PK of multiple SC doses of APL-2 in subjects with paroxysmal nocturnal hemoglobinuria (PNH) who have not received treatment with eculizumab (Soliris)[®] in the past.

An exploratory objective of the study is to assess the pharmacodynamics (PD) of multiple SC doses of APL-2 when administered to PNH subjects. See “Study Endpoints” in [Section 5.2](#).

5.2 Study Endpoints

Primary Safety Endpoint:

The primary safety endpoints of the study are the number and severity of treatment emergent adverse events (TEAEs) following administration of multiple doses of SC APL-2.

Primary Efficacy Endpoints:

- Change from baseline in LD
- Change from baseline in Haptoglobin
- Change from baseline in Hb

Secondary Endpoints:

- APL-2 plasma concentrations (and PK parameters as appropriate)
- Change from baseline in FACIT Fatigue Scale score
- Change from baseline in reticulocyte count
- Change from baseline in total bilirubin
- Number of RBC transfusions per month
- Change from baseline in Linear Analog Scale Assessment (LASA) for Quality of Life

Exploratory PD markers include:

- Complement (CH50, AP50, and C3) levels
- C3 deposition on RBC cells
- Clonal distribution of PNH RBCs

6. STUDY DESIGN

This is a Phase IIa, open-label, multiple dose, study in patients with PNH who have not received eculizumab (Soliris)[®] in the past. A single cohort of subjects is planned for evaluation.

Safety will be assessed throughout the study; serial blood and urine samples will be collected for these assessments. Blood samples will be collected for the assessment of APL-2 PK. Additional samples for assessment of PD will also be collected.

The study will consist of four parts;

- Part 1: Subjects will receive APL-2 for 28 days.

- Part 2A: Following review of available safety, PK and PD data by the investigator and sponsor, subjects showing evidence of clinical benefit may progress to Part 2A of the study and continue to receive daily doses of APL 2 until Day 84.
- Part 2B: Following review of available safety, PK and PD data by the investigator and sponsor subjects showing evidence of clinical benefit may progress to Part 2B of the study and continue to receive daily doses of APL 2 until Day 364.
- Part 3: Safety follow up

[figure not shown]
Screening will take place within 30 days prior to the start of dosing on Day 1.

Subjects will be entered into Part 1 of the study on Day 1 at a time designated by the PI. Research nurses or other appropriately qualified research personnel will administer the SC infusions for a minimum of 3 days (Days 1-3) until the research nurse considers that the subject is both capable and confident to conduct self-administration. The subject will continue to self-administer infusions at the clinic on those days when a clinic visit occurs (Day 8, 15 and 22) and at an off-site location convenient to the subject on all other days up to Day 28 in Part 1. Following review of available safety, PK and PD data by the investigator and sponsor subjects demonstrating clinical benefit from the treatment may progress to Part 2A of the study and continue to receive daily doses of APL-2 until Day 84, and then may progress to Part 2B of the study and continue to receive daily doses of APL-2 until Day 364. Doses will be self-administered throughout this period at an off-site location convenient to the subject with the exception of Days 29, 36, 43, 57, 71, 85, 113, 141, 169, 197, 225, 253, 281, 309, and 337 where dosing is performed by the subject at the clinical site. If a subject has a sub-optimal clinical response during daily dosing with 270 mg APL-2, the dose may be increased up to 360 mg/day during part 2A, and doses will be administered at the clinical site every 2 weeks for the first 6 weeks after commencing the higher dose. After the conclusion of the treatment period (Day 364), subjects will enter Part 3 of the study and return to the clinical site for follow-up study procedures on Day 365, 379, and 393 and final study procedures at an Exit Visit on Day 414. See Study Flowchart in [Section 2](#).

The planned length of participation in the study for each subject is approximately 444 days (from Day -30 through completion of the Day 414 Exit visit procedures). Interim PK and PD analyses may be performed to reconsider the sampling time points as the study progresses.

An independent Safety Monitoring Committee (SMC) will assess the progress and cumulative safety/tolerability data of the study on a regular basis.

Continuation of treatment – Decision scheme

7. SUBJECT SELECTION

The study will be conducted alongside the ongoing Phase Ib study APL2-CP-PNH-204 (PADDOCK) to investigate APL-2 in PNH patients who have not previously received treatment with eculizumab. Safety and efficacy data from both studies will be used to support the data obtained in the Phase III confirmatory study. Up to 20 subjects will be enrolled to complete 28 days of dosing.

7.1 Inclusion Criteria

At Screening (unless otherwise specified), subjects must fulfill all of the following inclusion criteria to be eligible for participation in the study:

1. At least 18 years old (inclusive)
2. Diagnosed with PNH (WBC clone >10%)
3. Lactose dehydrogenase ≥ 2 times the upper limit of normal
4. Screening Ferritin \geq normal and Total Iron Binding Capacity (TIBC) \leq LLN based on central lab reference ranges. If a subject is receiving iron supplements at screening, the investigator must ensure that his/her dose has been stable for 8 weeks prior to enrolment and must be maintained throughout the study (see [Section 8.4.4](#))
5. Last transfusion within 12 months prior to screening
6. Platelet count of $>30,000/\text{mm}^3$ at the screening visit
7. Absolute neutrophil count $>500/\text{mm}^3$ at the screening visit
8. Women of child-bearing potential (WOCBP) must have a negative pregnancy test at screening and must agree to use protocol defined methods of contraception for the duration of the study
9. Males must agree to use protocol defined methods of contraception and agree to refrain from donating sperm for the duration of the study
10. Vaccination against Neisseria meningitides types A, C, W, Y and B, Streptococcus pneumoniae and Haemophilus influenzae Type B (Hib) either within 2 years prior to Day 1 dosing, or within 14 days after starting treatment with APL-2. Unless documented evidence exists that subjects are non-responders to vaccination as evidenced by titers or display titer levels within acceptable local limits
11. Willing and able to give informed consent

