8. STUDY TREATMENTS

8.1 Allocation to Treatment

Each subject will be assigned a unique identification number upon screening. Subjects who complete the study screening assessments and meet all the eligibility criteria will be scheduled to enter the study and receive study treatment.

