8.4.4 Iron Supplements

For subjects receiving iron supplements at the time of APL-2 initiation, iron supplement doses should be maintained stable throughout the study unless iron levels (ferritin and TIBC) increase to unacceptable levels above ULN during the study. Change in dose of iron supplementation should be discussed with the Sponsor prior to implementation

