10.1.7.3 Serum Chemistry

- Blood urea nitrogen (BUN)
- Creatinine
- Estimated creatinine clearance (using Cockcroft-Gault formula) – screening only
- Bilirubin (total and direct)
- Albumin
- Aspartate aminotransferase (AST)
- ALT
- Uric acid
- Glucose
- Sodium

- Alkaline phosphatase (ALP)
- Lactate dehydrogenase (LD)
- Haptoglobin
- Gamma-glutamyl transpeptidase (GGT)
- Creatine kinase (CK)
- Potassium
- Chloride
- Ferritin
- B12/folate
- Total Iron Binding Capacity (TIBC)

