12.2 Statistical Analysis Methodology

A formal Statistical Analysis Plan (SAP) will be developed and finalized prior to locking the database. The full details of data presentations and analyses will be provided therein. Additional statistical analyses other than those described in this section may be performed if deemed

appropriate and included in the SAP. Any deviations from the final analysis plan or from what is outlined in the protocol will be discussed in the final study report.

No formal inferential statistics will be applied to data collected in the study.

The data from this study will also be pooled with the Cohort 2 data from the Phase Ib study APL2-CP-PNH-204 (PADDOCK), which also investigates 270mg/day APL-2 in PNH patients who have not previously received treatment with eculizumab. The details of reporting this pooled data will be documented in a separate SAP.

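### Does the TIBC entry limit, together with a Safety/ITT set that the SAP widens without saying so, put the four-subject analysis at risk?

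*Protocol*

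**What the plan says.** Protocol 7.1 states that "subjects must fulfill all of the following inclusion criteria to be eligible for participation in the study". Item 4 has two laboratory limbs, "Screening Ferritin \geq normal" and "Total Iron Binding Capacity (TIBC) \leq LLN based on central lab reference ranges", and the synopsis repeats both. The protocol's abbreviation list defines LLN as the lower limit of normal. Section 8.1 adds that subjects who "meet all the eligibility criteria will be scheduled to enter the study and receive study treatment". Section 8.4.4, on iron supplements, keeps the dose stable "unless iron levels (ferritin and TIBC) increase to unacceptable levels above ULN during the study".

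On analysis sets, protocol 12.2.1.2 makes the Safety Population those who were eligible for study medication and received at least one dose, with ITT identical. SAP 4.2 requires only the dose, and SAP 4.3 again makes ITT identical. The PK and PD sets are drawn from the Safety set in both documents.

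SAP section 15 says that, because enrolment closed after 4 subjects, only part of the protocol's analyses will be reported. It is silent on set definitions. Protocol 12.2 states: "Any deviations from the final analysis plan or from what is outlined in the protocol will be discussed in the final study report".

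**The concern.** There are two separate oddities, and they appear to reinforce each other.

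The first is the entry limit. If the ferritin limb means at or above the lower limit, a subject with both iron tests in the normal range is ineligible unless TIBC sits exactly on its lower limit. No reason is given. Section 8.4.4 speaks of ferritin and TIBC rising above the upper limit together, whereas criterion 4 bounds them in opposite directions. A reader may suspect that a different limit was meant, and that sites applied one.

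The second is the word *eligible* in protocol 12.2.1.2. If a site read criterion 4 loosely and dosed a subject with an in-range TIBC, the protocol's definition taken literally removes that subject from every analysis set except the Screened set. The SAP keeps the subject, and section 15 does not say that the definition changed. With 4 subjects, each is a quarter of the data. The range flag in SAP 7.2 would not help, because an in-range TIBC is unflagged even though it fails the criterion.

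**Working it through.** **Step 1: the criterion as printed.** Inputs: the TIBC limb of protocol 7.1 item 4 and the flagging rule in SAP 7.2.

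| Screening TIBC | Meets the limb? | Flagged as out of range? |
|---|---|---|
| below LLN | yes | yes |
| equal to LLN | yes | no |
| above LLN, up to ULN | no | no |
| above ULN | no | yes |

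The reading is correct: every in-range value except one equal to LLN fails.

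**Step 2: is the criterion contradicted elsewhere?** The synopsis and section 7.1 agree. Section 8.4.4 answers another question, namely when a supplement dose may change on study, and sets no entry limit. A subject may enter with TIBC at or below LLN and later exceed ULN, so both texts can hold at once. The pairing is awkward, but it is not a contradiction. The documents do not rule out a deliberate low-TIBC rule, and I take no view on which limit was intended.

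**Step 3: what the two set definitions give.** Inputs: 4 enrolled (SAP sections 1 and 3.4), all assumed dosed; k = dosed subjects who failed any entry criterion. The documents do not give k. Protocol n = 4 − k; SAP n = 4.

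| k | Protocol n | SAP n |
|---|---|---|
| 0 | 4 | 4 |
| 1 | 3 | 4 |
| 2 | 2 | 4 |
| 3 | 1 | 4 |
| 4 | 0 | 4 |

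At k = 1, dropping a subject with value x moves the mean m of four to m + (m − x)/3, and a share of 3/4 (75.0%) becomes 2/3 (66.7%) or 3/3 (100%). These figures describe any data set of four and failure of any entry criterion. They say nothing about whether k exceeds 0 here.

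**Step 4: is there evidence that k > 0?** None. Protocol 8.1 and 9.1 and SAP 3.2 all require the criteria to be met before treatment. The flow chart places an entry-criteria review on Day 1, and protocol 13.2.1 has the monitor check case report entries against source.

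**Step 5: would a case be seen?** Ferritin and TIBC are in the chemistry panel (protocol 10.1.7.3), and chemistry is drawn at screening. SAP 7.2 lists all laboratory data, and SAP 13.1 says the same of all data. For four subjects that is four screening TIBC values to read. In such a listing an unflagged TIBC is informative in itself: it is in range, so it fails the limb unless it equals LLN. SAP 5.1 lists each subject's analysis sets. SAP 5.8 has the sponsor's team review deviations during the study and before lock, and then lists them.

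**Step 6: would correcting the text change a result?** The SAP definition would be kept, since removing a treated subject from a safety population over an entry deviation is not defensible. Every planned table, plot and listing would therefore be the same.

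**The case for a change.** The strongest case for acting is that the mismatch between the two documents is certain even though its effect is not. One word governs the Safety, ITT, PK and PD sets. Section 15 of the SAP is the natural place to declare a changed definition, and its reference to a subset of analyses describes outputs that were dropped, not a set that became wider. No planned output compares TIBC with the criterion directly, and a site that misread the item might log no deviation. Declaring the change would cost one sentence.

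The factual part stands: the definitions differ and section 15 is silent. The rest does not lead to a change. The disclosure duty in protocol 12.2 is attached to the final report, so silence in section 15 does not breach it. The same section leaves full analysis detail to the SAP, which is the later document and makes the better choice. The worry about hidden deviations gives too little weight to the full listings and to the sponsor's review before lock. As to pooling with the Phase Ib study, "The details of reporting this pooled data will be documented in a separate SAP". That SAP is not among the documents, so nothing can be said about the definition it uses.

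**Conclusion.** The observation is accurate, but it does not call for a change to the plan. The Safety/ITT difference is a wording gap that the SAP fills sensibly by analysing everyone who was dosed. Its size is nil if k = 0. If k > 0, the SAP's n = 4 is still the set to report, so no planned number moves. Criterion 4 is unusual and its ferritin limit is loosely stated, but it is consistent between the synopsis and section 7.1 and is not contradicted by section 8.4.4. With enrolment closed, rewording it would affect no future subject. How it was applied is a matter for ordinary reporting of deviations.

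This rests on three assumptions: that all 4 enrolled subjects were dosed; that eligibility in protocol 12.2.1.2 means meeting the section 7 criteria, which is the natural reading although that section does not define it; and that the listings and deviation review are carried out as SAP 5.8, 7.2 and 13.1 describe. Because the study is descriptive, with no formal inference, an abbreviated report and primary-endpoint plots that identify each subject, a reader of the report could see any affected subject without a revised plan.

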7.1.1 Approved methods of contraception

Approved methods of contraception include: oral contraceptives, intrauterine device, medically acceptable barrier methods (diaphragm or condom), implantable or injectable contraceptives (like Norplant or DepoProvera) or removable birth control device (like NuvaRing or Evra patches); and/or surgical sterilization (at least 6 months before dosing). Subjects practicing abstinence and coitus interruptus (pull out method) must agree to use an approved method of contraception during the study.

7.2 Exclusion Criteria

Subjects will be excluded from the study if there is evidence of any of the following criteria at screening or check-in, as appropriate.

1. Prior eculizumab (Soliris®) treatment
2. Active bacterial infection
3. Hereditary complement deficiency
4. History of bone marrow transplantation
5. Concurrent SAA, defined as currently receiving immunosuppressive therapy for SAA including but not limited to cyclosporin A, tacrolimus, mycophenolate mofetil or anti-thymocyte globulin

6. Participation in any other investigational drug trial or exposure to other investigational agent, device or procedure within 30 days
7. Evidence of QTcF prolongation defined as >450 ms for males and >470 ms for females at screening
8. Breast-feeding women
9. History of meningococcal disease

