4.1.3.3 Toxicology

The toxicological potential of APL-2 has been investigated in repeat-dose toxicity studies in rabbits and monkeys across three routes of administration (SC, IV, IVT) under a testing strategy designed to facilitate differentiation between potential changes attributable to APL-2 per se and those attributable to the PEG40 domain of the drug molecule.

Daily subcutaneous administration of APL-2 and PEG40 for a duration of 6 months in rabbits and 9 months in monkey were associated with little systemic toxicity noted in either species beyond observations in the kidney (noted below). APL-2 and PEG40 were weakly to mildly immunogenic in rabbits, but not significantly immunogenic in monkeys. Single- or multi-tissue (or multi-organ) macrophage vacuolation was consistently observed in both species, and generally comparable in incidence and severity between APL-2- and PEG40-treated groups; thus, it was concluded the finding were caused by the PEG40 domain present within APL-2. Renal tubular degeneration was observed with a higher incidence in the monkey 9-month study in APL-2-treated animals compared to the PEG40-treated ones and was concluded to be APL-2 related.

The no-observed-adverse-effect-level (NOAEL) for SC-administered APL-2 was <1 mg/kg/d in rabbits and approximately 7 mg/kg/d in monkeys after 6- and 9-month chronic dosing, respectively.

Intravenous arms included in the 28-day repeat-dose SC studies of APL-2 in rabbits and monkeys suggested that IV-administered APL-2 was well-tolerated in both species, with only vacuolation of

tubular epithelial cells in the kidney observed microscopically in rabbits (which, again, was deemed to be caused in part by the PEG40 domain of APL-2). IV APL-2 was mildly immunogenic in rabbits (albeit less than what was observed by the SC route), and without immunologic effects in monkeys. The no-observed-effect-level (NOEL) by the IV route of administration for both rabbits and monkeys was determined to be ≥ 42 mg/kg after two doses separated by 14 days.

Repeated intravitreal administration (i.e. once every 4 weeks) of APL-2 to monkeys for up to 9 months was well-tolerated and revealed no drug-related systemic or ophthalmological changes. APL-2 may be minimally immunogenic when administered intravitreally, as evidenced by a single monkey having a marginal titer of APL-2 antibodies. The NOEL by the IVT route of administration for monkeys was determined to be ≥ 24.8 mg/eye.

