4.1.4 Clinical Data

To date, two Phase I studies in healthy volunteers have been conducted in order to assess safety and PK parameters of APL-2 administered as single and multiple dose SC injections and to guide dose selection for clinical studies in PNH subjects.

A single Phase I single ascending dose study has evaluated intravenous dosing of APL-2 in healthy volunteers.

A further five Phase I studies evaluating APL-2 delivered by SC injection are either planned or ongoing. These include two studies in healthy volunteers, a study in subjects with severe renal impairment and two ongoing clinical studies in PNH patients.

A phase IIa study in patients with autoimmune hemolytic anemia is also ongoing.

Table 1 summarises the information for all completed and ongoing studies evaluating systemic administration of APL-2.

Table 1: Summary of all clinical studies of systemically administered APL-2 (up to September 2017)

Protocol Number /Phase/Status	Protocol Title	Study Population Subjects Planned/Treated	Endpoints	Planned Dosage Regimen
SUBCUTANEOUS				
APL-CP0713-1 Phase I Complete	Phase I, Double-blind, Randomized, Single Ascending Dose Study in Healthy Volunteers	31 healthy volunteers APL-2: 24/24 Placebo: 7/7	Safety, tolerability, PK and PD of single ascending doses (SAD) of APL-2	SAD: 45, 90, 180, 360, 720, 1440 mg Single dose
APL-CP1014 Phase I Complete	Phase I, Double-blind, Randomized, Multiple Ascending Dose Study in Healthy Volunteers	20 healthy volunteers APL-2: 16/6 Placebo: 4/4	Safety, tolerability, PK and PD of multiple ascending (MAD) doses of APL-2	MAD: 30, 90, 180, 270 mg/day for 28 days
APL2-CP-PV-205 Phase I Ongoing	A Phase I, Single-Dose, Open-Label Study to Evaluate the Effect of Renal Impairment on the Pharmacokinetics of APL-2	8 subjects with severe renal impairment and 8 matched controls APL-2: 16/1	Comparative PK between subjects with severe renal impairment and matched controls	270 mg single dose
APL2-101 Phase I Ongoing	A Phase I, Double-Blind, Randomized Study of Daily, Twice-Weekly and Once-Weekly APL-2 in Healthy Volunteers	22 Healthy Volunteers APL-2: 16/0 Placebo: 6/0	Safety, tolerability, PK and PD of APL-2	360 mg daily 1300 mg twice weekly 2600 mg weekly

Protocol Number /Phase/Status	Protocol Title	Study Population Subjects Planned/Treated	Endpoints	Planned Dosage Regimen
				TBD (Final Cohort if dosed)

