4.1.5 Completed Clinical Studies in Healthy Volunteers

The two completed clinical studies investigating the safety, tolerability and PK of single (APL-CP-0713-1) and multiple (APL-CP-1014) SC doses of APL-2 in healthy volunteers showed that overall, single doses of APL-2, up to a dose of 1440 mg, and repeated daily doses of APL-2 up to a dose of 270 mg, appeared safe and well tolerated when administered to healthy volunteers by SC injection.

¹ One subject is included in 3 cohorts and is counted three times and one subject is included in two cohorts and is counted twice.

² One subject is included in 2 cohorts and is counted twice.

³ One subject received only a single dose of 180 mg then withdrew consent.

Serum APL-2 concentrations generally increased linearly with dose. APL-2 was slowly absorbed into the systemic circulation with median T_{max} values between 4.5 and 6 days across the dose groups. APL-2 serum concentration declined in a steady mono-exponential manner with a consistent rate of decay across two studies for all dose groups. Both studies demonstrated a slow terminal elimination with median $t_{1/2}$ values between 8 and 10 days.

Plasma complement C3 increased with increasing dose and a general dose-dependent reduction in AP50 was observed following multiple dosing with APL-2. Pharmacodynamic (PD) observations were consistent with a conclusion that APL-2 interacts with complement C3 and inhibits its activation.

Further details can be found in the current APL-2 Investigator's Brochure.

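### Cockcroft-Gault clearance is calculated at screening, but no entry criterion uses it or any other kidney measure, although a monkey kidney finding was judged APL-2 related

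*Protocol*

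**What the plan says.** Section 7.1 states that "subjects must fulfill all of the following inclusion criteria to be eligible for participation in the study", and 7.2 that "Subjects will be excluded from the study if there is evidence of any of the following criteria at screening or check-in". The laboratory items in the two lists are LD, ferritin and TIBC, platelets, neutrophils and the pregnancy test; QTcF also has a numerical limit. Section 8.1 then schedules anyone who completes screening and meets the criteria to enter and be treated.

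A kidney measure is available at that moment. The chemistry panel in 10.1.7.3 includes "Estimated creatinine clearance (using Cockcroft-Gault formula) – screening only".

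On the kidney itself, 4.1.3.3 reports: "Renal tubular degeneration was observed with a higher incidence in the monkey 9-month study in APL-2-treated animals". The comparison was with animals given PEG40, and the finding was attributed to APL-2. The same section puts the chronic monkey NOAEL at about 7 mg/kg/d. Table 1 in 4.1.4 lists APL2-CP-PV-205, a "Study to Evaluate the Effect of Renal Impairment on the Pharmacokinetics of APL-2". It was a single 270 mg dose study, ongoing in a table that runs to September 2017, with the entry "8 subjects with severe renal impairment and 8 matched controls APL-2: 16/1", that is, 16 planned and 1 treated.

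**The concern.** Screening yields a clearance value on which no entry rule acts. The kidney is an organ with a chronic animal finding that the sponsor attributes to the drug, and severe renal impairment is a group in which the sponsor had begun a separate single-dose PK study. As written, the protocol would let such a patient start daily dosing on the strength of the listed criteria alone.

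At stake is the safety of a small number of subjects with the least kidney reserve. No analysis or estimate in the SAP depends on it.

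**Working it through.** The plan states no figure on this point that could be reproduced. The check is a reading of the criteria and safeguards, with a little arithmetic.

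1. **Entry criteria.** Inclusion criteria that mention creatinine, clearance, renal impairment or dialysis: 0 of 11. Exclusion criteria: 0 of 9. Total: 0 of 11 + 9 = 20. The synopsis lists agree. Neither list has a general clause letting the investigator exclude a subject on medical judgement.

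2. **Other uses of the clearance value.** No other rule in the protocol or SAP refers to it.

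3. **What entry permits.** Part 1 gives 28 daily doses of 270 mg: 28 × 270 = 7,560 mg, against one dose of 270 mg in APL2-CP-PV-205. By September 2017 that study had treated 1 of 16 subjects (1/16 = 6%). From Day 29 the dose may rise to 360 mg/day (8.3.2), and dosing may run to Day 364. Parts 2A and 2B each require a review first, so 364 days is a ceiling and 28 days is what entry itself allows.

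4. **Safeguards, set against a subject whose kidney function is low but stable on Day 1.**

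| Safeguard | When it acts | What it responds to |
|---|---|---|
| Chemistry with creatinine and BUN (flow chart, 10.1.7.3) | Day 1 pre-dose, then Days 8 to 43 weekly, Days 57, 71 and 85 at 14-day intervals, then every 28 days (113 − 85 = 28) | Values are recorded; no threshold is set |
| Adverse event rules (11.1) | After dosing | A condition present at screening is medical history unless it worsens |
| Special-interest event (11.5) | After dosing | A clinically significant decrease in kidney function |
| Reviews before Parts 2A and 2B (section 6) | After Day 28 and after Day 84 | Clinical benefit and available safety, PK and PD data |
| SMC (9.6.1) | First meeting within 3 months of the first subject | Cumulative safety, laboratory and PK data |
| Removal of subjects (9.7) | After entry, by discretion | Substantial risk to the subject |

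None of these stops the first dose because of the screening clearance. Low function that is present and stable on Day 1 is neither an adverse event under 11.1 nor a special-interest event under 11.5.

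5. **Cost of an exclusion.** The documents do not give the share of otherwise eligible patients with severe renal impairment. At assumed shares of 2%, 5% and 10%, the loss from 20 planned subjects is 20 × 0.02 = 0.4, 20 × 0.05 = 1 and 20 × 0.10 = 2.

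**The case against.** The best defence is that the sponsor knew of the kidney finding and chose to manage it by monitoring. Chemistry is weekly for the first six weeks, PK is sampled on Days 1, 2, 3, 8 and 22, the SMC sees predicted exposures, and kidney decline is a special-interest event. Section 4.3 judges the proposed doses safe on up to 9 months of preclinical dosing and calls for a careful weighing of risk and benefit. AST, ALT, GGT and coagulation are also measured at screening without an entry limit, and a screening clearance is useful as a baseline. Much of this stands. A value collected without a threshold is not in itself a defect, and a decline on treatment would be looked for early. What remains is that all of it works after dosing has begun.

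A reader might infer that renal impairment would carry exposure past the monkey NOAEL. Section 8.3.2 puts 360 mg/day at about 85% of a monkey NOAEL Cmax, so a rise of 1/0.85 = 1.18-fold would reach it. If exposure is proportional to dose (4.1.5: "Serum APL-2 concentrations generally increased linearly with dose"), 270 mg/day sits at 0.85 × 270/360 = 0.64, and the rise needed is 1/0.6375 = 1.57-fold. The documents do not support the inference. They give no exposure ratio for renal impairment and do not say that the kidney clears APL-2. The monkey study behind the 85% is not named, and 4.1.3.2 reports non-linear absorption at higher doses in animals. Passing a NOAEL Cmax is also not the same as reaching a toxic exposure.

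Nor does slow washout make the kidney case stronger. Half-life "values between 8 and 10 days" is a healthy-volunteer figure, and it bears equally on any reason for stopping.

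A reader might also take the renal study to have been open, with 1 subject treated, when the protocol was issued on 31 January 2018. The table runs only to September 2017, and the later status is not given.

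**Conclusion.** The gap is real and confined to entry: 0 of 20 criteria use a kidney measure, so severe renal impairment alone would not keep a subject from 28 days of daily APL-2, or from longer dosing if the later reviews allow it. The reason to close it is the drug-related monkey finding together with the limited experience in severe renal impairment that Table 1 shows. No excess exposure or harm has been demonstrated, and its size cannot be estimated from the documents.

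This is a worthwhile, low-cost improvement to the protocol as written. Enrolment closed at 4 subjects (SAP section 1), so the practical reach was small, and nothing here implies that any of the four had impaired kidneys. The Investigator's Brochure and some protocol text between 4.1.5 and 4.2 were not available. If either gives a reason for having no threshold, the point reduces to stating that reason in 7.2 or 4.3.

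**What to change.** Add one exclusion to 7.2, and to the matching synopsis list: severe renal impairment by screening Cockcroft-Gault clearance, for example below 30 mL/min. That cut-off is an assumption for the sponsor to confirm, since the documents supply none. State that the criterion will be revisited when APL2-CP-PV-205 reports.

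The value is already calculated, so no extra sample or visit is needed. The cost is the loss of a few otherwise eligible patients in a rare disease: between 0.4 and 2 of 20 on the assumed shares above. The change cannot alter the entry of the 4 subjects already enrolled.
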